9.4.2.2. Analysis of The Main Estimator

The proportion of responders will be compared between the 2 arms using, if possible, the stratum-adjusted Mantel-Haenszel test on the difference of proportions, with the following stratification factors: presence of compensated cirrhosis at screening (yes or no, for Part 1 only), HDV RNA testing laboratory location (China versus outside of China), and HBeAg status at screening (positive versus negative).

9.4.3. Key Secondary Endpoints

The key secondary endpoints at Week 48 are defined as follows:

1. Proportion of participants with HDV RNA $\geq 2 \log_{10}$ IU/mL decline from baseline or HDV RNA TND at Week 48.
2. Proportion of participants with normal ALT levels at Week 48.
3. Proportion of participants with HBsAg seroclearance at Week 48.
4. Proportion of participants with ≥ 2 kPa reduction from baseline in LSM assessed by VCTE (FibroScan) at Week 48.

The 4 key secondary endpoints are binary and will be analyzed using, if possible, the stratum-adjusted Mantel-Haenszel test similarly to the primary efficacy endpoint with corresponding 95% CIs on the difference of proportions between the 2 arms.

The estimand, estimator, and missing data handling rules will be constructed for and applied to each of the key secondary efficacy endpoints in a similar fashion as described earlier for the primary efficacy endpoint. The details are presented in the SAP.

9.4.4. Other Efficacy Endpoints

Descriptive statistics will be used for all efficacy endpoints which will be summarized by intervention arm over time and by study phase, using the whole study data as well as by stage (defined in Section 9.4.2.2). Specific endpoints may be analyzed using suitable categorical data approaches (eg, Mantel-Haenszel test, logistic regression for proportions or other categorical type of endpoint), longitudinal repeated measures or ANCOVA models (eg, for continuous types of variables), or survival analysis based on the Kaplan-Meier estimates (for time-to-event variables), as appropriate.

The statistical inference to compare the efficacy between Arm 1 and Arm 2 as measured by the other secondary endpoints at Week 48 will utilize the weighted inverse normal combination method as described for the primary efficacy endpoint. No further adjustment for multiplicity will be made and no imputation rule will be used in case of missing data. More details are provided in the SAP.

The efficacy of JNJ-3989 +NA during study intervention and follow-up phases will be evaluated in terms of the proportion of participants with

- HDV RNA $\geq 2 \log_{10}$ IU/mL decline from baseline or HDV RNA TND in combination with normal ALT,
- HDV RNA $\geq 2 \log_{10}$ IU/mL decline from baseline in combination with normal ALT,
- HDV RNA TND in combination with normal ALT,
- HDV RNA $\geq 2 \log_{10}$ IU/mL decline from baseline or HDV RNA TND,
- HDV RNA $\geq 2 \log_{10}$ IU/mL decline from baseline,
- HDV RNA TND,
- Normal ALT,
- Off-treatment sustained HDV RNA response,
- Off-treatment sustained HDV RNA relapse,

will be tabulated by intervention arm as well as over time. The comparison among the intervention arms for these endpoints at Week 48 will be done using MH chi-square test stratified by the stratification factors and corresponding 95% CIs without adjustment for multiple intervals. The time to reach HDV RNA $\geq 2 \log_{10}$ IU/mL decline or HDV RNA TND will be summarized based on Kaplan-Meier estimates in tables and graphs.

In addition, descriptive statistics on values and changes from baseline over time in HDV RNA and ALT will be summarized by intervention arm.

The proportion of participants with HBsAg seroclearance/seroconversion during the study intervention and follow-up phases will also be tabulated by intervention arm, and over time.

The proportion of participants with HBV virologic breakthrough, the proportion of participants with HBV flare (virologic, biochemical, and clinical) post end of treatment, and the proportion of participants with sustained HBV response off-treatment after stopping JNJ-3989 treatment will be tabulated by intervention arm over time.

The change in the liver fibrosis from baseline measured by LSM according to VCTE (FibroScan) at end of JNJ-3989 treatment and during follow-up will be tabulated by intervention arm over time.

In addition, subgroup analyses will be conducted to evaluate the potential association between treatment outcome and selected demographic and baseline characteristics (including but not limited to age, presence of compensated cirrhosis at screening, HDV genotype, baseline values for HDV RNA, ALT, and HBsAg, etc). Multivariate model analyses with exploration of interaction terms might also be performed. The primary and key secondary efficacy endpoints, respectively, will be analyzed by means of a logistic regression model. Exploratory descriptive summaries will be displayed by subgroups with corresponding 95% CIs without multiplicity adjustment. Forest plots will be used for the graphical displays. Subgroup analyses, as exploratory, might be conducted on Part 2 data alone as well as combined data (Part 1 and Part 2) to leverage the total sample size of the entire study.

The HBV blood markers such as HBsAg, HBeAg (for HBeAg-positive participants only), HBV DNA during study intervention and follow-up will also be summarized and plotted in terms of values and changes from baseline over time by intervention arm. The proportion of participants with HBsAg, HBeAg (for HBeAg-positive participants only) and HBV DNA levels as well as changes from baseline below/above different cut-offs will be analyzed as appropriate over time by intervention arm. Time-to-event endpoints, such as time to reach HBsAg <1 IU/mL, will be summarized based on Kaplan-Meier estimates in tables and graphs.

The proportion of participants who reach undetectability of HBV RNA and/or HBcrAg during the study intervention and follow-up phases will also be tabulated by intervention arm. In addition, time to undetectability will be summarized based on Kaplan-Meier estimates in tables and graphs. Descriptive statistics on values and change from baseline in HBV RNA and HBcrAg levels will be summarized by intervention arm.

Graphic data displays will also be used to summarize the efficacy data by intervention arm and over time. In addition, the potential association between HBsAg and HDV RNA will be explored graphically over time.

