At the time of initial protocol writing, efficacy was assessed using snapshot data through 26 March 2020. Antiviral activity data were available for 56 CHB participants who received 3 SC injections of 25 to 400 mg JNJ-3989 every 4 weeks. The antiviral activity data showed that administration of JNJ-3989 at doses of 25 to 400 mg resulted, on average, in pronounced HBsAg decline which was generally sustained at least until Day 168 (ie, 16 weeks after last dose) across all doses. No apparent dose response was observed at doses between 100 and 400 mg JNJ-3989; a numerically smaller mean decline was observed at the lower doses of 25 and 50 mg, mainly apparent after end of JNJ-3989 dosing. Treatment status (ie, virologically suppressed or not treated) did not seem to affect HBsAg changes. Other measurable serological and virological markers (HBV DNA, HBV RNA, HBeAg, hepatitis B core-related antigen [HBcrAg]) also showed responses to JNJ-3989, indicating that JNJ-3989 shows target activity on all detectable viral products. Refer to the latest IB¹⁵ for the most recent efficacy data.

Part 1 REEF-D Study Data (Study 73763989HPB2004)

Of the 22 participants with CHD enrolled into Part 1 of the REEF-D study, 17 were randomized to treatment with JNJ-3989 100 mg + NA and 5 were randomized to placebo + NA. The predefined antiviral activity criteria to start Part 2 of the study (at least 8 JNJ-3989 treated participants with ≥ 0.5 log reduction from baseline in HBsAg and HDV RNA and 4 of those with ≥ 1 log reduction in HDV RNA) were met.

The second interim analysis (IA) was performed when all Part 1 participants (N = 22) had reached Week 48 or later, or discontinued earlier.

REEF-D Safety Data at Week 48 for Part 1

At Week 48, 6/17 (35.3%) participants in the JNJ-3989 + NA arm were reported with a Grade ≥ 3 AE.

Adverse events were considered related to JNJ-3989 by the investigator in 11/17 (64.7%) participants who received JNJ-3989 + NA treatment.

Among the adverse events of special interest (AESIs) defined in the study protocol, ALT/AST elevations were reported in 13/17 (76.5%) participants in the JNJ-3989 + NA arm and no participants in the placebo + NA arm. For 2 of these 13 participants, the ALT elevation criteria according to the protocol were not met nor the discontinuation criteria for JNJ-3989. One additional participant met the ALT elevation criteria and discontinued JNJ-3989, but the event was not reported as an AE.

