During follow-up, 4/11 (36.4%) participants in the JNJ-3989 + NA arm reported treatment-emergent AEs, which were AESIs (ie, ALT/AST elevations).

No deaths were reported. Two (11.8%) participants in the JNJ-3989+NA arm experienced 3 SAEs: ALT increased and AST increased in 1 (5.9%) participant, and transaminases increased in 1 (5.9%) participant, which lead to withdrawal from study drug.

Twelve of 22 (54.5%) participants enrolled in Part 1 experienced ALT elevations on treatment up to the 48-week timepoint; all 12 were treated with JNJ-73763989 + NA. These ALT elevations were Grade 3 in 5 participants and Grade 4 in 7 participants. The mean (SD) change from baseline was 5.6 (80.05) U/L. The majority of these ALT elevations had a peak of ALT between 120 and 650 U/L. A single case marked a peak of 1,162 U/L, which showed levels below 1,000 U/L on confirmatory tests. None of the participants with ALT elevations showed signs of decreased hepatic function, but 1 participant showed clinical symptoms of epigastric pain, nausea and vomiting for 4 days during the peak of ALT elevation. Management of these acute elevations was following protocol-defined criteria. Some of the cases showed a prolonged pattern of ALT elevation for which no management criteria were provided in the protocol at the time of the event.

No clinically significant safety ECG or vital sign findings were observed.

REEF-D Efficacy Data at Week 48 for Part 1

In all JNJ-3989-treated participants, treatment with JNJ-3989 led to reductions in HBsAg, and subsequently, HDV RNA.

At Week 48, 4/17 (23.5%) participants in the JNJ-73763989 + NA and none in the NA arm achieved the primary composite endpoint of HDV RNA decline from baseline of ≥ 2 log₁₀ IU/mL (or undetectable) and normal ALT. Among the 5 participants without ALT elevations in the JNJ-73763989+NA arm, 4/5 (80.0%) participants achieved the primary composite endpoint, of which 2/5 (40.0%) participants had HDV RNA <LLOQ.

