8.3.6.1. Intervention-emergent ALT/AST Elevations

Management of intervention-emergent ALT/AST elevations is presented graphically in Section 10.6, Appendix 6: Intervention-emergent ALT/AST Elevations, and is described below.

Any intervention-emergent elevation of ALT and/or AST $\geq 3x$ ULN and $\geq 2x$ nadir (ie, lowest value during study participation) should trigger an assessment of confounding factors (alcohol intake, change in concomitant medication, and comorbidities) and should trigger a confirmatory study visit to repeat laboratory testing as specified below. Repeat laboratory values should include AFP, ALT, AST, ALP, bilirubin (total and direct), INR, albumin, HBV DNA, and HDV RNA. Additional tests should be considered based on clinical judgement (refer to Section 10.6, Appendix 6: Intervention-emergent ALT/AST Elevations). The confirmatory visit should be scheduled preferably within 3 days of the receipt of the initial ALT/AST results.

Weekly basis monitoring (or more frequently as long as values increase) until ALT/AST levels have returned to $< 3x$ ULN or $< 2x$ nadir, and if present, liver related symptoms have improved. With ALT and/or AST values $\geq 3x$ ULN and $\geq 2x$ nadir, visit intervals may be extended to 14 days if values have been stable or decreasing on three consecutive visits. The participant will be monitored (laboratory testing of ALT, AST, ALP, bilirubin [total and direct], INR, albumin,

HBV DNA, and HDV RNA) on a weekly basis or more frequently until ALT and/or AST levels have returned to 50% of the maximal value.

Note: In case of urgency, local laboratory assessments could be considered. In case of IWRS participant unblinding and if the investigator requires to be unblinded in case of an emergent safety event (ie, study intervention discontinuation due to ALT flares) to allow further treatment of the participant, a sponsor request can be made to have the investigator and sponsor unblinded to all HDV RNA and HBsAg data from the double-blind phase. Off-treatment local HDV RNA test can be done to exclude/assess for HDV-driven flare.

Management of intervention-emergent ALT and/or AST elevations:

JNJ-3989 treatment should be stopped, and NA treatment needs to be continued in the following situations:

- Participants with liver cirrhosis:
 - Confirmed ALT/AST elevation $>5x$ ULN and $\geq 2x$ nadir
 - ALT/AST elevation $\geq 3x$ ULN and $\geq 2x$ nadir for >4 weeks.

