9.4.2.1. Primary Estimand

The main analysis of the primary endpoint will be addressed by using the following estimand attributes:

1. Study Intervention:

- Arm 1: JNJ-3989 + NA
- Arm 2: Placebo + NA

2. Study population: Participants 18 to 65 years of age, inclusive, with HBV/HDV co-infection

3. Variable: Response status defined as having HDV RNA decline $\geq 2 \log_{10}$ IU/mL from baseline or HDV RNA TND in combination with normal ALT at Week 48

4. Intercurrent events (ICEs):

- a. Treatment discontinuation prior to Week 48: if the participant discontinued treatment prior to Week 48 then the participant will be considered as non-responder (composite strategy).
- b. Selected major protocol deviations (identified as ICEs): participants who experienced major protocol deviations considered ICE and who have missing ALT and/or HDV RNA data for the primary endpoint at Week 48 will be considered as non-responders (composite strategy).
- c. Deaths prior to Week 48 are handled in a composite strategy as participants who die prior to Week 48 will be considered as non-responders.

5. Population level summary: Difference in proportion of responders between the 2 intervention arms (Arm 1-Arm 2).

Note: The SAP will list the major protocol deviations used for the purpose of efficacy analyses and flag those that are to be considered ICEs.

Assumptions:

- Missing Data for HDV RNA and ALT are Missing At Random (MAR)
- The treatment effect is homogeneous across strata.

Data Included

All available data from randomized participants that have received at least one dose is included (ITT analysis set in Part 2), after taking into account all the ICEs and applying the ICE strategies.

Missing Data Handling Rules

Participants who withdraw from the study prior to Week 48 will be considered as non-responders.

If a participant remains in the study after early discontinuing treatment or after experiencing a major protocol deviation (defined for the purpose of efficacy analyses and is an intercurrent event) and has missing Week 48 value for HDV RNA and/or ALT, then the imputation to non-response will be applied. If the value for the primary endpoint at Week 48 is available, then such data will be used to determine their response status.

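### The no-imputation rule for other secondary endpoints at Week 48 gives the primary composite and two key secondary endpoints a second missing-data rule with no stated denominator, which can raise the Arm 1 composite rate

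*Protocol*

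**What the plan says.** Protocol Section 9.4.4, on the comparison of Arm 1 with Arm 2 for the other secondary endpoints at Week 48, states: "No further adjustment for multiplicity will be made and no imputation rule will be used in case of missing data". The synopsis (Section 1.1) repeats this. Section 9.4.4 then lists the responder endpoints to be compared at Week 48 by a stratified Mantel-Haenszel test with 95% confidence intervals. The first is the primary composite (HDV RNA response together with normal ALT). HDV RNA response alone and normal ALT alone are also listed; both are key secondary endpoints.

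For the primary endpoint, Section 9.4.2.1 sets a different rule: "Participants who withdraw from the study prior to Week 48 will be considered as non-responders". A participant who stops treatment early, stays in the study and has no Week 48 value is also set to non-response. Other missing values are multiply imputed. Section 9.4.3 carries this over to the key secondary endpoints: "missing data handling rules will be constructed for and applied to each of the key secondary efficacy endpoints in a similar fashion".

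Section 9.4.1 names ITT as the primary efficacy set. No section says what the denominator is when an other secondary endpoint is missing at Week 48.

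**The concern.** One quantity at one visit has two missing-data rules. Keeping a participant with no value in the denominator of a responder rate amounts to counting non-response, which is itself an imputation. The natural reading of a no-imputation rule is therefore observed cases, and the tables could show two different Week 48 rates for the same composite.

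The two rates would not differ at random. Section 8.3.6.1 lists ALT/AST elevations for which "JNJ-3989 treatment should be stopped, and NA treatment needs to be continued in the following situations". In Part 1 these elevations were confined to the active arm and went with failure on the composite. If such participants lack a Week 48 value, the observed-case rate describes mainly those who tolerated the drug. In a descriptive study the estimates are the product, so the stake is a misleading estimate.

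**Working it through.** **Inputs, all from Section 2.2.3 (Part 1, Week 48 interim analysis)**

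- Arm sizes: "17 were randomized to treatment with JNJ-3989 100 mg + NA and 5 were randomized to placebo + NA".
- Composite response: "At Week 48, 4/17 (23.5%) participants in the JNJ-73763989 + NA and none in the NA arm achieved the primary composite endpoint".
- On-treatment ALT elevations: 12 of 22 participants, all 12 on JNJ-3989, so 12/17 against 0/5.
- Composite response among the 5 active participants without ALT elevations: 4/5.

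**Reproducing the plan's figures.** 4/17 = 23.5%; 4/5 = 80.0%; 12/22 = 54.5%. All agree with the text.

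**Responders among participants with flares.** Active responders overall minus those without flares: 4 − 4 = 0, so 0/12. The protocol does not say how many of these 12 had an observed Week 48 value, so 0/12 may already count some missing values as non-response. The calculation below is unaffected.

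**Effect of no imputation.** Let k be the number of active participants with flares who have no Week 48 value. None of them is a responder, so the observed-case rate is 4/(17 − k). Under the primary endpoint's rule, if these k stopped treatment or withdrew, the rate stays 4/17 whatever k is. Placebo stays at 0%.

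| k | Observed cases | Rate | Rate under the primary rule |
|---|---|---|---|
| 0 | 4/17 | 23.5% | 23.5% |
| 2 | 4/15 | 26.7% | 23.5% |
| 4 | 4/13 | 30.8% | 23.5% |
| 6 | 4/11 | 36.4% | 23.5% |
| 8 | 4/9 | 44.4% | 23.5% |

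The rate rises with every increase in k, and the arm difference rises with it.

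**Part 2 illustration.** Arm 1 has about 24 participants (Section 4.1). The number of responders is an assumption, shown as a range; the missing participants are taken to be non-responders.

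| Assumed responders | ITT, r/24 | 4 missing, r/20 | 8 missing, r/16 |
|---|---|---|---|
| 4 | 16.7% | 20.0% | 25.0% |
| 6 | 25.0% | 30.0% | 37.5% |
| 8 | 33.3% | 40.0% | 50.0% |

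Part 2 excluded cirrhosis and tightened entry on HBsAg and HDV RNA, so the Part 1 flare and response proportions need not carry over.

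**The case against.** The strongest reply is that stopping JNJ-3989 does not make data missing. Under Sections 7.1 and 7.2, participants who stop are not automatically withdrawn; they enter follow-up, where the schedule samples HDV RNA and liver tests, and flares trigger extra testing. This stands, and it means k may be small. It does not make k zero. In the double-blind schedule Week 48 shares a column with the early withdrawal visit, follow-up visits may be timed from that visit, and Section 9.4.4 summarises by study phase. A later value can therefore be placed under follow-up rather than Week 48. Withdrawals and missed visits add to this.

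A second reply is that ITT is the efficacy set and details are deferred to the SAP, so unimputed counts over ITT would give 4/17, as in Section 2.2.3. The denominator is indeed unstated. The no-imputation rule, however, is fixed in the protocol, and an SAP that counted missing values as non-response would contradict it.

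A reader might infer three stronger things, none supported by the documents:

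- **That the Part 1 rate could plausibly reach 4/6 = 66.7%.** This subtracts the 11 in "During follow-up, 4/11 (36.4%) participants in the JNJ-3989 + NA arm reported treatment-emergent AEs" from 17. Those 11 were under follow-up, some may have stopped after Week 48, and the number lacking a Week 48 value is not given. It also needs all four responders to lie outside the 11.
- **That 13 of 30 Part 2 participants (11 completed, 2 in follow-up) measure missingness.** That is the status in March 2024, after the double-blind phase, with no split by arm. It says nothing about Week 48 values.
- **That the time course and follow-up responses are inflated too.** The no-imputation sentence belongs to the Week 48 comparison; no rule is stated for the other tables.

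**Conclusion.** The point holds for the binary other secondary endpoints at Week 48. The protocol fixes a rule for them that conflicts with the rule for the same quantities as primary and key secondary endpoints, and it leaves the denominator open.

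For the composite, the direction follows from the protocol's Part 1 data: missing flare participants can only raise the Arm 1 rate and the arm difference. The size depends on k. It is 0 points at k = 0, 30.8 − 23.5 = 7.3 points at k = 4 and 44.4 − 23.5 = 20.9 points at k = 8. This assumes an observed-case reading and that the missing participants are those with flares.

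The direction is not shown for endpoints based on HDV RNA alone, and for relapse it may differ. Primary and key secondary results keep their own rules and are unaffected. Because the analyses are descriptive, no type I error is at issue. The change is worth making because it is cheap and prevents two Week 48 rates for one endpoint.

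**What to change.** In Sections 9.4.4 and 1.1, replace the no-imputation wording for binary other secondary endpoints at Week 48. Apply the primary endpoint's intercurrent-event and missing-data rules, with the ITT denominator, and show observed cases as supplementary.

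Section 9.4.2.1 describes in two ways a participant who stops early but has a Week 48 value: the intercurrent-event list makes that participant a non-responder, while the missing-data rules use the value. Whichever is adopted for the primary endpoint should apply here too, so that the rates agree.

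For open-label and follow-up tables, report n/N with the denominator stated. Do not extend the non-responder rule to visits that Amendment 5 removed administratively in Part 2; that would turn participants whose treatment was shortened by sponsor decision into failures.

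The cost is a sentence in each of two sections, a few extra table rows, and Arm 1 rates that may look slightly less favourable. No new data are needed.

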9.2. Sample Size Determination

The sample size in Part 1 (N = 20) is primarily driven by the objectives of Part 1 to provide sufficient evidence of safety and early antiviral activity of JNJ-3989 and to exclude futility of the regimen in a small number of HBV/HDV co-infected participants before initiating the larger Part 2 of the study. No formal statistical power calculations were conducted for Part 1.

A total sample size of 130 participants for Part 2 in the original protocol would yield a statistical power >90% to detect a between-arm difference of $\geq 26\%$ in the primary efficacy endpoint at Week 48, at a 1-sided Type 1 error rate of 0.025, based on the test for the between-arm difference

in proportions with the normal approximation. Per Protocol Amendment 4, the sample size in Part 2 was reduced to 30 participants.

In the original protocol, sample size re-estimation was planned at the single IA during Part 2 to allow for an increase to a maximum of 170 participants in Part 2 for the conditional power at the end of the study to be at least 80% in case the assumed 0.04 response rate for placebo was too conservative. Due to reduction in sample size per Protocol Amendment 4, the single IA with sample size re-estimation was removed.

In the original protocol, the number of participants included in this study was planned to be a minimum of approximately N 20 (if Part 2 is not initiated) or between a minimum of N 165 and a maximum of N 190 if Part 2 is initiated. Per Protocol Amendment 4, the planned number of participants included in the study will be N 20 in Part 1 and N 30 in Part 2.

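### The unconditional logistic regression in the subgroup analysis will usually have no finite treatment odds ratio for the primary endpoint, because about 6 Part 2 controls at a 4% response rate leave the placebo cell empty

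*Protocol*

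**What the plan says.** The subgroup paragraph of Section 9.4.4, repeated in the Synopsis under Other Secondary and Exploratory Endpoints, gives an open list of baseline characteristics: age, compensated cirrhosis, HDV genotype, and baseline HDV RNA, ALT and HBsAg. On models it says: "Multivariate model analyses with exploration of interaction terms might also be performed". It then says: "The primary and key secondary efficacy endpoints, respectively, will be analyzed by means of a logistic regression model". The first of these sentences is optional and the second is not. Part 2 alone and both parts combined are both named as possible data sets. Descriptive subgroup summaries with 95% intervals, and forest plots, are also planned.

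Sections 9.4.2.2 and 9.4.3 specify the stratified Mantel-Haenszel test for the same endpoints, but only where it is possible. The logistic sentence has no such qualifier.

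Section 9.2 gives one control rate, for the primary endpoint: "the assumed 0.04 response rate for placebo". It also records the cut of Part 2 from 130 to 30. Section 4.1 puts the reduced arms at about 24 and 6 and excludes cirrhotic participants from Part 2. For Part 1 at Week 48, Section 2.2.3 reports that "4/17 (23.5%) participants in the JNJ-73763989 + NA and none in the NA arm achieved the primary composite endpoint", with 17 and 5 randomised.

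**The concern.** A logistic model has a finite maximum-likelihood treatment odds ratio only if each arm contains at least one responder and one non-responder. For a treatment-by-subgroup interaction the same must hold in every arm-by-subgroup cell. With about six controls and a 4% response rate, the control cell is expected to be empty. The likelihood then keeps rising as the treatment coefficient grows, and software either stops or prints a large arbitrary value with a meaningless Wald interval.

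Sections 9.4.2.2 and 9.4.3 allow for sparse data defeating the Mantel-Haenszel test. The logistic model depends at least as heavily on filled cells, yet it is required outright. At stake is whether any treatment or interaction odds ratio from the subgroup models could be interpreted. Baseline HBsAg and HDV RNA will draw attention, since Sections 2.3.1.2 and 2.3.3 tie them to the risk of ALT elevations.

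**Working it through.** **Inputs.** Placebo rate 0.04 and difference 0.26, hence 0.30 on active (Section 9.2). Original Part 2 size 130 at 4:1, hence 104 and 26 (arithmetic). Reduced Part 2 arms about 24 and 6 (Section 4.1). Part 1 primary endpoint 4/17 and 0/5 (Section 2.2.3).

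**The plan's own figure.** Section 9.2 claims power above 90% "at a 1-sided Type 1 error rate of 0.025". Unpooled normal approximation: SE = √(0.04×0.96/26 + 0.30×0.70/104) = 0.0591; 0.26/0.0591 − 1.96 = 2.44; power 99.3%. With the pooled variance, power is 89.6%. The stated inputs are therefore consistent with the claim, and 0.04 and 0.30 are used below.

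**No placebo responder, primary endpoint.** P = (1 − p)^n.
- Part 2 as reduced: expected responders 6 × 0.04 = 0.24; P = 0.96^6 = 0.783.
- Part 2 as first planned: 0.96^26 = 0.346.
- Parts 1 and 2 combined, given the observed 0/5: again 0.96^6 = 0.783. Ignoring the Part 1 result it would be 0.96^11 = 0.638.

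**Finite treatment odds ratio, Part 2.** (1 − 0.96^6 − 0.04^6) × (1 − 0.70^24 − 0.30^24) = 0.217. Using 4/17 for the active rate also gives 0.217, so the control arm decides it. As an illustration, 7/24 versus 0/6 has a sample odds ratio of (7/17)/(0/6), which is infinite; a maximum-likelihood fit to that table failed with a singular matrix.

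**Interaction with a binary subgroup.** With placebo split 3/3, the chance that both placebo cells contain a responder and a non-responder is (1 − 0.96^3 − 0.04^3)^2 = 0.1152^2 = 0.013. At a placebo rate of 0.10 it is 0.073. For 11 pooled controls split 5/6, ignoring the observed 0/5, it is 0.040.

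**Sensitivity to the placebo rate (6 controls).**

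| Placebo rate | P(no responder) |
|---|---|
| 0.02 | 0.886 |
| 0.04 | 0.783 |
| 0.10 | 0.531 |
| 0.15 | 0.377 |
| 0.20 | 0.262 |
| 0.30 | 0.118 |

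The probability falls below one half once the rate exceeds 1 − 0.5^(1/6) = 0.109. The rates other than 0.04 are assumptions. They cover the key secondary endpoints, for which the protocol states none.

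**Information for several factors at once.** Expected pooled responders on the primary endpoint: 4 + 24 × 0.235 + 0.24 = 9.9, or 4 + 24 × 0.30 + 0.24 = 11.4 at the planning rate.

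**Cirrhosis.** Section 9.4.4 lists it as a subgroup factor and allows Part 2 alone, but Section 4.1 excludes cirrhotic participants from Part 2. There it takes one value and has no estimable coefficient.

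**The case against.** Several stronger readings are tempting, and the document does not support them.

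- *The protocol fixes an ordinary maximum-likelihood fit.* It says only that a logistic regression model will be used. Firth-penalised and exact fits are logistic regression too, and the SAP, which is not at hand, may name one. What stands is that the sentence is unconditional and that following it with the usual fit would usually fail.
- *All key secondary endpoints fail as well.* The 4% applies to the primary endpoint only. HDV RNA response and normal ALT are components of that composite, so their placebo rates cannot be lower and may be much higher. An empty cell is plausible for HBsAg seroclearance, since Section 2 calls HBsAg loss on available therapy low without giving a figure. It is not shown for normal ALT or the 2 kPa stiffness reduction.
- *The forest plots would show non-existent odds ratios.* The intervals are attached to descriptive subgroup summaries, and nothing ties the plots to the logistic model.
- *A model with all listed factors is planned.* The list is open, no simultaneous model is stated, and multivariable and interaction models are optional. The Amendment 4 log also names subgroup analyses among those made optional.
- *The cut created the interaction problem.* With 26 controls split 13/13, the chance of a placebo cell with no responder was already 1 − (1 − 0.96^13)^2 = 83%. The cut changed the treatment main effect, from 35% to 78%.

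Part of the purpose also survives. With no placebo responders, only treatment and its interactions diverge; baseline main effects are still estimated, in effect from the active arm. Finally, the protocol itself provided for 0.04 being too conservative. A rate of 0.10 would still leave a 53% chance of an empty placebo cell in Part 2.

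**Conclusion.** The point holds for the primary endpoint. On the protocol's own 4% rate and about six Part 2 controls, a standard treatment odds ratio fails to exist in about 78% of cases, for Part 2 alone and for the pooled data given 0/5 in Part 1. The optional interaction with a binary subgroup would be estimable in about 1% of cases for Part 2, even with an even placebo split. For the key secondary endpoints the point is conditional: an empty placebo cell is more likely than not only if the placebo rate is below about 11%. The cirrhosis factor is unusable in Part 2-only models at any rate.

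The result assumes independent responses at a common placebo rate of 0.04, six placebo participants in Part 2, and a maximum-likelihood fit. Severity is minor, because all analyses are now descriptive and the subgroup analysis is exploratory. No primary conclusion depends on it.

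**What to change.** In Section 9.4.4 and the matching Synopsis paragraph, replace the unconditional logistic sentence as follows.

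1. Report responder counts by arm and subgroup with exact (Clopper-Pearson) intervals, for Part 2 and for the pooled data.
2. Where a model is fitted, use Firth-penalised or exact logistic regression with treatment and one baseline factor at a time, with profile-likelihood or exact intervals. If placebo has no responders, an exact interval for the treatment odds ratio will be open at the upper end and should be shown so.
3. Fit multivariable or interaction models only if every arm-by-subgroup cell contains both responders and non-responders.
4. Drop cirrhosis from Part 2-only models.

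The change is to wording and table shells and needs no new data. It gives up interaction and multivariable odds ratios that these data would rarely support. It has one real cost: under Section 6.3 participants are unblinded once they complete Week 48, and by Amendment 5 all were past the double-blind phase. The change should therefore be labelled as made after unblinding and as exploratory, with the reason given as cell counts and not observed effects.
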